### **Secondary Outcome**

To determine the cognitive side effects we will use the following neuropsychological battery:

- Mini- Mental State Examination (MMSE),
- Postictal Recovery of Orientation,
- Rey Auditory Verbal Learning Test (RAVLT)

- Autobiographical Memory Interview – Short Form (AMI – SF),
- Subjective Memory Questionnaire (SMQ),
- Reading subtest of the Wide Range Achievement Test, 3rd Edition (WRAT-3)
- The Stroop Color Word Test (SCWT) (Golden version)
- Trail Making Test Part A & B
- Wechsler Adult Intelligence Test-Third Edition (WAIS-III), Digit Span Subtest
- WAIS-III Digit Symbol
- Controlled Oral Word Association Test (COWAT)
- N-Back

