### **Hypothesis**

We hypothesize that patients who receive ketamine anesthesia during ECT will need fewer treatments to achieve remission. At the end of the ECT course they will display fewer cognitive side effects compared to those treated with methohexitol anesthesia.

In the imaging part of this study, the main theoretical question is whether ECT exerts its effect primarily by altering networks. Our specific hypothesis is that ECT will decrease functional connectivity in the Default Mode Network.

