#### b. Favorable cognitive side effects profile

Moderate impairment of short-term memory (STM) is a concerning side effect of ECT. Several recent reports suggest that ketamine anesthesia may have a cognitive-sparing effect on memory function following ECT. The NMDA glutamate receptor mediates long-term changes in synaptic strength, i.e. long-term potentiation (LTP), responsible for memory formation. Antagonism of the NMDA receptor by ketamine may prevent the LTP-blocking hippocampal structural changes induced during a tonic-clonic seizure. This suggestion is rooted in animal studies indicating that ketamine prevents brain damage in the amygdala, piriform cortex and CA1 region of the hippocampus during status epilepticus, as well as protects from seizure-induced impairment of rat hippocampal LTP.

Krystal et al demonstrated less cognitive side effects following ECT when patients were anesthetized with ketamine instead of methohexitol. The primary measure of cognitive function was the extent of retrograde amnesia, the most common cognitive side effect of ECT. They also observed a more rapid cognitive recovery time after ECT in patients anesthetized with ketamine as opposed to methohexitol. This is particularly notable because methohexitol has a shorter duration of action than ketamine and it represents preliminary evidence that ketamine anesthesia may prevent STM loss after treatment.

McDaniel et al noted improved memory function of a patient treated with ketamine anesthesia for ECT when compared with the same patient's previous ECT treatment using etomidate anesthesia. Hypothesizing that patients treated with ketamine anesthesia for ECT will have less

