### b. Assessment Instruments

The primary outcome measure is the HRSD-24 which will be administered at baseline and before each treatment. The HRSD-24 is a semistructured interview designed to rate the severity of depressive symptoms in patients with a primary depressive illness. We will use the 24-item version, which includes three items in addition to the original 21 (i.e., Helplessness, hopelessness, worthlessness).

Brief Psychiatric Rating Scale (BPRS) (Hillside Anchored version) BPRS will be administered at screening and after last ECT treatment.

Psychotic symptoms will be measured by the four item positive symptoms subscale (consisting of suspiciousness, hallucinations, unusual thought content, and conceptual disorganization) of the Brief Psychiatric Rating Scale (BPRS). After each ECT treatment BPRS+ will be administered as following: after full orientation recovery, two hours post ECT. If any of the items are positive (2 or higher) BPRS+ will be re administered at 4 hours post ECT. If symptoms persist, patients will be further evaluated by a study psychiatrist and will be treated clinically as needed. Of note, that as part of standard care, patients are under constant observation and monitoring after ECT until they are deemed stable to be discharged from the unit.

**Clinician-Administered Rating Scale for Mania (CARS-M):** The CARS-m is a brief, clinician-administered, semistructured interview, which rates presence versus absence of a symptom, its severity, and symptom change in response to treatment. It is used to characterize manic behavior, but also to capture psychotic symptoms. These items yield two subscale scores one for mania (items 1-100 and one for psychosis (items 11-15).

The secondary outcome measures are the scores of neuropsychological (NP) battery. The neuropsychological (NP) battery is administered to all subjects at baseline (prior to the first ECT), on ECT #4 and following the end of the acute phase of ECT. In addition the MMSE will be performed prior to each ECT session and assessment of postictal recovery of orientation after each ECT session.

The neuropsychological test battery consists of the following instruments:

- Reading subtest of the Wide Range Achievement Test, 3rd Edition (WRAT-3), which will only be administered at baseline
- Mini- Mental State Examination (MMSE)
- Postictal Recovery of Orientation
- Rey Auditory Verbal Learning Test (RAVLT)-Immediate

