### **13. Data Analysis**

To test whether the time to remission is different between the ketamine and the methohexitol groups, a survival analysis will be performed. The outcome event will be remission, and Kaplan-Meier curves will show the percent of patients not in remission as a function of time on study. A log-rank test will be used to test for differences between the time to remission in the two groups. Patients who drop out of the study prior to achieving remission or who continue to the end of the study period without achieving remission will be analyzed as censored at the time of last observation.

For Aim 1, to test whether the rate of change in the HRSD score over time is different in the two treatment groups, a mixed model for longitudinal data will be used. The fixed effects are

treatment group and time on study, and the random effect is subject. The data will be examined to see whether a linear function of time is appropriate. If not, either the data will be transformed to achieve linearity, or another form (e.g., quadratic) of model will be considered. This model will yield estimates for slopes (rates of change in HRSD scores per visit) for each treatment group, and the groups will be compared by testing whether the slopes are significantly different from one another.

For Aim 2, to test whether the rate of change in the various measures of cognitive function over time is different in the two treatment groups, a mixed model for longitudinal data will be used for each of the measures. As above, the fixed effects are treatment group and time on study, and the random effect is subject. The data will be examined to see whether a linear function of time is appropriate. If not, either the data will be transformed to achieve linearity, or another form (e.g., quadratic) of model will be considered. As above, the model will provide estimates of the slopes measuring the rates of change in scores per visit for the two treatment groups; and the treatments will be compared by testing for a difference between the slopes corresponding to the two groups.

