Since this is a pilot study, the goal is to estimate the magnitude of the effect sizes for use in designing a subsequent study. With 12 patients randomized to each of the two treatment groups, there is only 45% power with an alpha level of 5% to detect a difference of 50% remission rate in the methohexital group and an 80% remission rate in the ketamine group at visit 8. For the other aims, which look at the change in scores on various rating scales over time, there will be 80% power with an alpha level of 5% (2-sided) to detect a difference between the slopes (measuring rate of change in scores on tests per visit) for the two treatment groups of magnitude  $0.05\sigma$ , where  $\sigma$  is the standard deviation of scores in either treatment group at a single visit. If, for example, the standard deviation of the HRSD scores is 5.0, then there will be power to detect an increased rate of improvement in the ketamine group of 0.25 points per visit, corresponding to an average improvement of 2.0 more points per 8 visits in the ketamine group than whatever improvement is observed in the methohexital group (Diggle et al 1995).

Given the recognition that, with the small sample size, power will be low, the primary focus of analysis is to determine whether ECT with ketamine anesthesia compared to ECT with methohexital anesthesia produces a clinically significant effect, i.e., one that, even if it does not reach statistical significance, would justify a larger clinical trial to replicate effect size. We expect a mean number of 8 treatments to remission based on the results of a Consortium for Research in ECT paper.

Our specific hypothesis is that ECT will decrease functional connectivity in the Default Mode Network (time-wise hypothesis). We also think that the decrease in the expression of this network will correlate with the effectiveness of the ECT, or at least will show a difference

between responders and non-responders (group-wise hypothesis). In order to detect network changes, we will calculate seed based correlation, ICA network expressions and amplitude measures of the networks.

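### Eleven repeated cognitive instruments each get a 5% test with no lead measure: the chance of a false signal favouring ketamine is about 7% to 26%, depending on their correlation, against 2.5% for one test

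*Combined protocol and SAP*

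**What the plan says.** The Hypothesis section makes one directional prediction about cognition: "At the end of the ECT course they will display fewer cognitive side effects compared to those treated with methohexitol anesthesia". It names no instrument.

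The Secondary Outcome section says "To determine the cognitive side effects we will use the following neuropsychological battery" and lists 12 instruments. Section 7b (Assessment Instruments) defines the outcome as the whole set: "The secondary outcome measures are the scores of neuropsychological (NP) battery". No score is ranked first and no composite is defined. One of the 12, the WRAT-3 reading subtest, is described in the same section as a test "which will only be administered at baseline".

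For Aim 2, section 13 states that "a mixed model for longitudinal data will be used for each of the measures" and that the treatments are compared by testing for a difference in slopes. The level appears in the power paragraph of that section, which covers the rating-scale aims together: "there will be 80% power with an alpha level of 5% (2-sided) to detect a difference between the slopes". No hierarchy or multiplicity adjustment is given for cognition. The cluster-level correction under Amplitude measures applies to imaging maps only.

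**The concern.** One directional claim is served by about a dozen separate tests. Nothing says in advance which score would support the claim, or how a single significant score among several null ones would be read. A result on any one of memory, attention, fluency or orientation could then be offered as evidence of cognitive sparing, at an error rate above the nominal one. The Significance section says that even minimal cognitive sparing would matter, so a favourable result on one score is likely to be noticed.

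**Working it through.** **The plan's own figure.** The documents state no family-wise error rate. The only figure attached to these tests is 80% power for a slope difference of 0.05σ per visit, with 12 patients per arm. The usual formula is n per arm = 2(z_α + z_β)²σ²(1 − ρ)/(S_xx d²), where ρ is the within-patient correlation and S_xx the spread of the visit times. The documents do not give ρ, so the 80% cannot be reproduced. It does not enter the error calculation below.

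**Inputs.**
- Instruments listed: 12 (Secondary Outcome).
- Baseline only: WRAT-3 (section 7b). This leaves 12 − 1 = 11 repeated instruments, or 12 scores if Trail Making A and B are analysed separately.
- Level per test: 5% two-sided (section 13), so 2.5% in the direction of the hypothesis.
- Correlation between the test statistics: not given. Assumed equal for all pairs, at 0, 0.5, 0.7 and 0.9.

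**Independent scores.** The chance of at least one false signal favouring ketamine among k scores is 1 − 0.975^k.
- k = 11: 1 − 0.975^11 = 0.243
- k = 12: 1 − 0.975^12 = 0.262

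For a signal in either direction it is 1 − 0.95^k.
- k = 11: 1 − 0.95^11 = 0.431
- k = 12: 1 − 0.95^12 = 0.460

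**Correlated scores.** For equicorrelated normal statistics with correlation r and c = 1.96, the chance of at least one signal favouring ketamine is 1 − ∫ φ(t) · Φ((c − √r·t)/√(1 − r))^k dt. For either direction, the term raised to the power k becomes Φ((c − √r·t)/√(1 − r)) − Φ((−c − √r·t)/√(1 − r)). Numerical integration gives:

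| Assumed correlation | Favouring ketamine, 11 / 12 scores | Either direction, 11 / 12 scores |
|---|---|---|
| 0 | 24.3% / 26.2% | 43.1% / 46.0% |
| 0.5 | 15.2% / 16.0% | 30.4% / 31.9% |
| 0.7 | 11.2% / 11.6% | 22.3% / 23.2% |
| 0.9 | 6.6% / 6.7% | 13.1% / 13.5% |

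The reference values for a single test are 2.5% and 5%. The hypothesis is directional, so the first column of results is the relevant one. For 12 scores it runs from 6.7/2.5 ≈ 2.7 times to 26.2/2.5 ≈ 10.5 times the single-test rate.

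**After the fix.** One score named in advance and tested alone at two-sided 5% returns the error for that claim to 2.5% in ketamine's favour.

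**The case against.** The strongest reply is that this is a pilot. Section 13 says that its goal is to estimate effect sizes for a later study, accepts low power, and looks for an effect worth pursuing even without statistical significance. Cognition is secondary, and the mixed models already yield slope estimates by group. No decision rule turns one p-value below 0.05 into a cognitive conclusion. All of this stands, and it lowers the severity. It does not close the gap. The same section plans a formal test for every measure, with a stated level and power, in support of a directional hypothesis, and nothing labels the cognitive results descriptive.

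The error rates also depend on correlations that the documents do not supply. Independence is unlikely for scores taken from the same patients, so 26% is the top of the range for 12 scores. Even at 0.9 the rate is above 2.5%.

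Several stronger readings are tempting, but the documents do not support them:
- A reader might take 22–46% as the error rate of the cognitive-sparing claim. Those figures count signals in either direction, and the claim has one direction.
- A reader might say that a false signal is likely. Every figure above is below 50%.
- A reader might infer that cognitive sparing is a stated reason for the next trial. The Significance section does not mention a next trial. The Benefits section mentions possible cognitive benefit to participants and, separately, that the results will guide a larger study.
- A reader might count further tests from Stroop, RAVLT or n-back sub-scores. The plan does not say that these will be tested.
- A reader might infer that the protocol already points to the AMI-SF. The sentence "The primary measure of cognitive function was the extent of retrograde amnesia, the most common cognitive side effect of ECT" describes a cited earlier study. The same Background section opens with short-term memory and then argues at length from a second study of it, which supports the RAVLT as well.

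**Conclusion.** The point holds in a limited form. Eleven repeated instruments, or 12 scores, are each tested at two-sided 5% for one directional hypothesis, with no lead measure and no adjustment. The chance of at least one false signal favouring ketamine is about 7% to 26% over assumed correlations of 0.9 down to 0. This rests on no true effect on any score, equal correlations, normal test statistics and one test per score. It does not count the freedom in section 13 to choose the form of the time effect after looking at the data. The primary outcome is unaffected. The weakness is that, as planned, an isolated significant cognitive score could not be read at its nominal level.

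**What to change.** Before the data are unmasked for analysis, the sponsor names one lead cognitive score in section 13 and tests it alone at two-sided 5%. The Background supports either the AMI-SF, for retrograde memory, or the RAVLT, for short-term memory. The choice is the sponsor's. All other cognitive scores are reported as slope differences with 95% confidence intervals and labelled exploratory, which fits the pilot's aim of estimating effect sizes. The plan should add that no claim of cognitive sparing rests on those scores alone.

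WRAT-3 should be moved from the Secondary Outcome list to the baseline descriptors. This is editorial, since section 7b already restricts it to baseline. Adding it as a main-effect covariate is not needed, because it would do little for a comparison of slopes.

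The cost is a few lines of text, with no change to data collection or sample size. The downside is that a significant result on a score other than the lead is exploratory only.

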- Autobiographical Memory Interview – Short Form (AMI – SF)
- Subjective Memory Questionnaire (SMQ)
- The Stroop Color Word Test (SCWT) (Golden version)
- Trail Making Test Part A & B
- WAIS-III Digit Symbol
- Wechsler Adult Intelligence Test-Third Edition (WAIS-III), Digit Span Subtest
- Controlled Oral Word Association Test (COWAT)
- N-Back

The cognitive domains to be assessed include orientation/global functioning, verbal anterograde memory, autobiographical (retrograde) memory, and subjective memory.

**Global Functioning:** The Reading subtest of the Wide Range Achievement Test, Third Edition (WRAT-3) will be administered at baseline to provide an estimate of premorbid intellectual functioning. The reading score in particular has shown a moderate correlation with WAIS Full Scale IQ scores and provides a sufficient estimate of average IQ levels. This has also been found to be true among individuals exhibiting cognitive decline. The Mini-Mental State Exam (MMSE) is a measure of global cognitive functioning with a maximum score of 30. Reliability and validity have been well established and alternate forms are available.

**Orientation** Postictal recovery of orientation will be assessed following every ECT treatment utilizing the Sabin method. According to this method, once the patient gains spontaneous respiration, orientation will be continually assessed (in 15-minute intervals) by asking the patient

to state his/her name, age, date of birth, day of the week, and current location. The assessment will continue until the patient correctly answers all five questions or until a time limit of 90 minutes is reached.

**Memory:** One of the most sensitive formats of assessing anterograde verbal memory is word list learning, given its relative freedom of associative context. The Rey Auditory Verbal Learning Test (RAVLT) is brief and easy to administer and has been well-validated. Equivalent alternate forms are available.

Retrograde amnesia for autobiographical information will be assessed by the Autobiographical Memory Interview (AMI), which was originally developed by Weiner, Squire, and colleagues, and later expanded by Sackheim et al.

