### c. Timing of Assessments

**Table 2: Timing of Assessments**

Assessment	Baseline 	3X weekly before ECT	3X Weekly following ECT	ECT # 4	After last ECT 
Informed Consent	X				
Past Psychiatric History	X				
Medical Evaluation	X				
HRSD-24	X	X			X 
BPRS	X				X
BPRS positive items		X	X 		
SCID	X				
Neuropsychological Battery	X			X 	X 
Reorientation time			X		X
MMSE		X			
TESS	X				X

 Performed within 24 hours before the first ECT;  24hrs post ECT;  24-72 hrs post last ECT;

 1 week post last ECT  BPRS+ after full recovery, at 2h, at 4h if BPRS+2h >2

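### Postictal reorientation has no pre-treatment value, so the planned comparison of slopes misses an anesthetic effect to the extent that it is present from the first session and stays constant

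*Combined protocol and SAP*

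**What the plan says.** The Secondary Outcome section and section 7b (Assessment Instruments) both list postictal recovery of orientation in the cognitive battery. Section 7b requires "assessment of postictal recovery of orientation after each ECT session". It starts the clock after the seizure ("once the patient gains spontaneous respiration, orientation will be continually assessed (in 15-minute intervals") and stops it when all five questions are answered or "until a time limit of 90 minutes is reached". In Table 2 the row "Reorientation time" is marked only after treatments and after the last ECT; its baseline cell is blank. Section 7b also gives the battery as a whole a baseline administration, which cannot apply to a postictal measure.

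For the cognitive aim, section 13 states that "a mixed model for longitudinal data will be used for each of the measures". It specifies fixed effects of treatment group and time, a random subject effect, and one rule for all measures: "the treatments will be compared by testing for a difference between the slopes corresponding to the two groups". No test of the group term is named, and no separate analysis of reorientation is given.

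The background section on cognitive side effects says of an earlier comparison of the two agents: "They also observed a more rapid cognitive recovery time after ECT in patients anesthetized with ketamine". The Hypothesis section words the cognitive expectation as fewer side effects at the end of the course, which is a statement about level.

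**The concern.** For a measure with an untreated baseline, both groups start from the same expected value, so a later separation shows at least partly as a difference in slope. Reorientation has no such starting point. If one anesthetic shortens recovery by a similar amount at each session, the two groups follow parallel lines from session 1. The whole effect then sits in the group term, which is fitted but not named as the comparison, and the slope difference is zero.

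At stake is the effect size carried forward. Section 13 says that the pilot's goal is to estimate effect sizes for a later study. For a level effect on this measure, the planned contrast would estimate a value near zero.

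**Working it through.** **The plan's own figure.** Section 13 states 80% power (two-sided 5%) for a slope difference of 0.05σ per visit with 12 per arm. It gives neither the within-patient correlation ρ nor the number of visits, so the figure can be neither confirmed nor refuted. From n = 2(z_α + z_β)²σ²(1 − ρ)/(Sxx·d²), with n = 12, d = 0.05σ and 8 visits (Sxx = 42): 1 − ρ = 12 × 42 × 0.0025/(2 × 7.85) = 0.080, so ρ would have to be 0.92. The point below does not depend on this.

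**Algebra.** A patient's slope is Σ(t − t̄)y_t / Σ(t − t̄)². A shift δ at every session adds δΣ(t − t̄) = 0 to the numerator. The expected slope difference is therefore exactly zero for any δ.

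**Inputs.** From the documents: 12 per arm (section 13) and about 8 sessions (section 6). Assumed, because the documents give no SDs: within-patient SD 10 minutes, between-patient SD 5, 10 or 20 minutes, equal correlation between sessions, complete 8-session courses.

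**Constant shift, comparison of mean levels.** SE = √[(s_b² + 10²/8) × 2/12]; power from the noncentral t with 22 df, two-sided 5%.

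| Between-patient SD | SE (min) | Level test, 10 min | Level test, 15 min | Slope test, either shift |
|---|---|---|---|---|
| 5 | 2.50 | 97% | 100% | 5% |
| 10 | 4.33 | 60% | 91% | 5% |
| 20 | 8.29 | 21% | 41% | 5% |

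**Simulation in SD units** (20,000 runs, ρ = 0.3, 0.5, 0.7). For a 1 SD constant shift the slope test rejected in 5.1%, 5.1% and 5.0% of runs and the level test in 97%, 88% and 78%. At 2 SD the slope test was still at 5%. In 200 fits of a random-intercept model (1 SD shift, ρ = 0.5), group-by-time was significant in 4% and the centred group term in 89%. With an unshifted time-0 value added, the slope test would reject in 31% to 60% of runs at 1 SD, so the missing pre-treatment value accounts for the lost signal.

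**Measurement features.** With the 15-minute grid, the 90-minute limit, an assumed mean of 40 minutes and courses of 4 to 12 sessions (between- and within-patient SD 10), the slope test rejected in 4–5% of runs. The level test rejected in 58–60% (10 minutes) and 90–91% (15 minutes).

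**Effect absent at session 1 only, constant afterwards.** Dropping the effect at session 1 gives an expected slope difference of δ × 3.5/42 = δ/12. The SE of the slope difference is √[(100/42) × 2/12] = 0.63.
- Slope test: 10 minutes gives 0.833/0.63 = 1.32, power 24%; 15 minutes gives 1.25/0.63 = 1.98, power about 47%.
- Level test, between-patient SD 10, mean difference 7δ/8: 8.75/4.33 = 2.02, power 49% (48% in simulation); 13.125/4.33 = 3.03, power 83%.
- Level test, between-patient SD 20, 10 minutes: 8.75/8.29 = 1.06, power about 17%, which is below the slope test. The level test's advantage in this pattern therefore depends on the assumed SD.

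**The case against.** The strongest reply is that constancy is an assumption. A reader might infer from the background that ketamine speeds reorientation at every session by a fixed amount. The documents do not say so: they report faster recovery after ECT in one cited comparison, without naming session 1, a constant size or this instrument. There are also reasons to doubt constancy. Session 1 is a titration session, often with more than one stimulus. Anesthetic doses may be adjusted later. The Significance section calls the cognitive side effects of ECT cumulative, which is a pattern that a slope can pick up. This stands, and it makes the point conditional.

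A reader might also infer that a benefit would be lost or reported as no difference however large it was. That goes too far. The group term is in the model, the raw times are collected after every session, and section 13 says that interest extends to clinically relevant effects that miss significance. Nothing forbids reporting the group estimate. But it is not the stated comparison, and the option to transform or add a quadratic term changes the shape over time, not the contrast tested.

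Finally, section 13 does frame the cognitive question as a rate of change, and that is a legitimate question where a baseline exists. For reorientation it asks only whether the anesthetic effect changes over the course, not whether there is one.

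**Conclusion.** The point holds in conditional form. For postictal reorientation the planned slope test has no power beyond its 5% error rate against an effect that is present from session 1 and constant. This follows from the schedule and the stated contrast and needs no assumed SD. An effect that builds up, or is absent only at session 1, would show at least partly in the slope. The background makes a level effect plausible but does not settle which pattern to expect.

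The gain from a level comparison is uncertain, because it rests on assumed SDs: 21% to 97% power for a constant 10 minutes over the range shown, and 41% to nearly 100% for 15 minutes. The consequence is confined to one secondary measure in a 24-patient pilot; the primary outcome and study conduct are unaffected. It still deserves correction, because the purpose is effect-size estimation and the stated contrast would return roughly zero for a real level difference.

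**What to change.** In section 13, exempt postictal recovery of orientation from the slope rule. Name as its treatment contrast the group difference in mean level over sessions, in minutes with a confidence interval. Estimate it in the mixed model with group and session as fixed effects, a random subject effect and no group-by-session term. Leaving the interaction out matters: with it in the same model, the meaning of the group term depends on coding and weighting. Report the group-by-session (slope) difference from a separate model as a secondary description, so that a building effect is still seen.

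State in advance how session is coded, since courses may run to 15 sessions and late sessions will hold few patients, and how a patient not oriented at 90 minutes is scored.

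The cost is one or two sentences, with the same data and model family. The slope ceases to be the test for this one measure, so some power is given up if the effect mainly builds up over the course.

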### 1. Study Overview

This is a prospective, random assignment, double blind, parallel group pilot study comparing the efficacy of bifrontal ECT performed with ketamine anesthesia to that performed with methohexitol anesthesia in patients with a major depressive episode. We intend over a 2 year period, to recruit 24 patients who are scheduled to receive an acute course of ECT. Patients who are able and willing to provide written informed consent will be randomly assigned on a 1:1 ratio to receive either a course of bifrontal ECT using ketamine or methohexitol anesthesia. Subjects will receive a standard acute course of ECT (3X/week) and depressive symptomatology will be monitored with the Hamilton Rating Scale for Depression (HRSD-24) before each treatment.

The primary outcome will be the number of treatments needed to achieve remission. Remission is defined as two consecutive HRSD scores  $\leq 10$ , and HRSD total score does not change  $> 3$

points or remains < 6 at the last two consecutive treatments. For the secondary aim of this pilot study we will monitor cognitive changes before and after each ECT treatment, and at the end of the treatment course. In addition, we will collect data on other treatment parameters such as seizure duration, electroencephalogram (EEG) morphology, hemodynamic changes, and emergence of any psychotic symptoms post treatment.

Parallel with these procedures we will also collect magnetic resonance imaging (MRI) data on these subjects. The timeline of neuroimaging and its relation to ECT is illustrated in Figure 1.

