#### **4. Randomization**

**Method:** The permuted block method of randomization will be used to assign patients to one of the treatment conditions. Block size will be varied to minimize the likelihood that the blind will be broken by raters who are blind to assessment. For safety purposes the anesthesiologist and

the ECT psychiatrist will not be masked to the anesthetic agent used. Randomization will be performed by the research coordinator and will be communicated to the ECT psychiatrist and the anesthesiologist.

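### The slope models let the arms differ in mean at baseline, before any study anesthetic; a common baseline mean would recover some precision, by an amount that depends on an unstated correlation

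*Combined protocol and SAP*

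**What the plan says.** Section 13 (Data Analysis) specifies a mixed model for HRSD under Aim 1, with fixed effects of "treatment group and time on study, and the random effect is subject. The data will be examined" for linearity over time. It adds: "This model will yield estimates for slopes (rates of change in HRSD scores per visit) for each treatment group", and the arms are compared by testing whether those slopes differ. Aim 2 uses the same form for each cognitive measure: "As above, the fixed effects are treatment group and time on study, and the random effect is subject". No baseline covariate and no constraint on the baseline means is named, and the section does not say whether the baseline score is part of the response.

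On design, section 1 (Study Overview) has patients "randomly assigned on a 1:1 ratio", and section 4 says: "The permuted block method of randomization will be used to assign patients to one of the treatment conditions". Table 2 footnotes the baseline assessments as "Performed within 24 hours before the first ECT". Section 7b says the neuropsychological battery "is administered to all subjects at baseline (prior to the first ECT), on ECT #4", and again after the acute course. HRSD is rated at baseline and before every treatment.

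**The concern.** A group main effect beside arm-specific slopes gives each arm a free intercept at time zero. When time zero is a rating taken before any study anesthetic in randomised arms, the true intercept difference is zero. The model spends information estimating it, and the estimate is negatively correlated with the estimated slope difference.

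With 12 per arm, the chance difference in baseline means has standard deviation √(2/12) = 0.41σ, where σ is the standard deviation of a score at one visit. In the planned model the arm that happens to start worse tends to show the steeper improvement. Section 13 says that the goal is to estimate effect sizes for a later study and concedes low power, so precision in these contrasts is what the pilot has to offer.

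**Working it through.** **Inputs from the documents.** 12 per arm ("With 12 patients randomized to each of the two treatment groups"); two-sided alpha 5%; target slope difference 0.05σ per visit with a claimed 80% power; 8 visits in the worked example; subject as the only random effect, which implies an equal correlation ρ between any two visits.

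**Assumptions.** ρ is not stated, so 0.3 to 0.885 is shown. HRSD times are taken as 0 to 8 and battery times as 0, 4, 8. Data are complete, σ = 1, and power uses the normal approximation.

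**The plan's 80%.** With separate intercepts, Var(slope difference) = 2(1−ρ)/(12·Sxx), with Sxx = 60 for times 0–8. Power of 80% needs SE = 0.05/(1.960 + 0.842) = 0.01785, so 1−ρ = 360 × 0.01785² = 0.115 and ρ = 0.885. The figure cannot be confirmed, because ρ and the exact number of visits are missing. Times 0–10 would need ρ = 0.79, and times 0–15 would need 0.35. At ρ = 0.5 over times 0–8, power is 27%.

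**Effect of a common baseline mean.** Let V be the within-patient covariance matrix, and put a = 1′V⁻¹1, b = 1′V⁻¹t, c = t′V⁻¹t. Then:

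- separate intercepts: Var = 2/[12(c − b²/a)]
- common intercept: Var = 2/(12c)
- proportion of variance saved = b²/(ac)

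HRSD at ρ = 0.5: a = 1.8, b = 7.2, c = 148.8, so the saving is 51.84/267.84 = 19.4%. Battery at ρ = 0.5: a = 1.5, b = 6, c = 88, so the saving is 36/132 = 27.3%.

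| ρ | HRSD saving | HRSD power at 0.05σ | Battery saving | Battery power at 0.05σ |
|---|---|---|---|---|
| 0.3 | 33% | 20% → 28% | 40% | 13% → 19% |
| 0.5 | 19% | 27% → 32% | 27% | 16% → 21% |
| 0.7 | 10% | 41% → 45% | 16% | 24% → 28% |
| 0.885 | 3% | 80% → 81% | 6% | 53% → 56% |

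**Random slopes added** (slope variance 0.005 to 0.02σ², uncorrelated with the intercept). Across ρ 0.3 to 0.7 the saving is 2–23% for HRSD and 5–32% for the battery. At ρ = 0.885 it is 0.3–0.9% and 0.9–2.5%. A negative intercept–slope correlation raises it: at −0.3 and ρ = 0.885, it is about 11–12% for HRSD and 13–14% for the battery.

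**Without linearity.** With time categorical, the difference in change at the last visit has variance (2/12)·2(1−ρ) with separate baseline means and (2/12)(1−ρ²) with a common one. The ratio is (1+ρ)/2, or 0.65, 0.75, 0.85 and 0.94 at the four values of ρ. The gain therefore does not rest on straight lines.

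**Cost under strict linearity.** Suppose the arms separate by one unit straight after time 0 and then run parallel. The separate-intercept model reports an HRSD slope difference of 4/60 = 0.067. The constrained model reports 0.118, 0.097, 0.082 and 0.072 at ρ = 0.3, 0.5, 0.7 and 0.885.

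**The case against.** The strongest reply is that the planned model is standard and valid. With randomisation and a correct time shape, its slope contrast is unbiased and its interval already reflects chance baseline imbalance. The primary log-rank analysis is untouched. This stands: the point concerns efficiency, not error.

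The size is also open. If the plan's own 80% holds over times 0–8, ρ is about 0.885, and the HRSD gain is about one power point. That stands too, but this ρ is back-calculated rather than observed. It also leaves the battery at 53% power, although section 13 claims 80% for the rating-scale aims generally.

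The shift under linear time is a real drawback. The Rationale cites faster response with ketamine, and the background section on its antidepressant effect cites onset within two hours, so early separation is plausible here.

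Four stronger readings are tempting and are not supported:

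- That the group-by-time term is missing. The list of fixed effects does not name it, but a slope per arm and a test of their difference imply it.
- That the change costs nothing. The time-shape risk above is a cost.
- That it is worth up to 16 extra patients. That comes from one corner, the three-occasion battery at ρ = 0.3: 24/0.604 = 39.7.
- That baseline as a covariate on post-baseline values does the same job. For a slope test that keeps the group term, the covariate leaves the group-by-time coefficient alone, while dropping time 0 cuts Sxx from 60 to 42 for HRSD and from 32 to 8 for the battery. The slope variance rises 1.43-fold and 4-fold.

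**Conclusion.** The point holds as a recommendation on efficiency. As written, both models allow a baseline difference between arms that the design excludes, and removing it reduces the variance of the between-arm contrast whenever the time shape is right. The reduction runs from about 33% down to 3% for HRSD and from 40% down to 6% for the battery as ρ goes from 0.3 to 0.885. It is close to zero at high ρ with random slopes unrelated to the starting level. Without a stated ρ, no single figure can be given.

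The conclusion rests on baseline being the first response, which section 13 implies through rates of change but does not say, and on the assumed visit times and complete data. It does not extend to postictal reorientation, first measured after the randomised anesthetic, or to the WRAT-3, which is given only at baseline and has no slope.

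**What to change.** In section 13, state that the baseline score is part of the response. For HRSD and each cognitive score with a pre-ECT value, constrain the arms to a common baseline mean and keep the group-by-time contrast, written out explicitly for clarity. Name postictal reorientation and the WRAT-3 as exceptions.

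Fit time as categorical, or in a shape that has been checked. If time stays strictly linear, report the separate-intercept model as a sensitivity analysis, because the two will diverge if the arms separate early. Use baseline as a covariate on post-baseline values only if the target is changed from a slope difference to an adjusted mean difference.

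The change takes a few sentences of model specification and possibly one extra model per measure. It needs no further patients, visits or data. The price is reliance on the time shape.
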